3.4.3 Other Efficacy Analyses

[Redacted text block]

- █ [Redacted list item]
- █ [Redacted list item]
- █ [Redacted list item]
- █ [Redacted list item]
- █ [Redacted list item]
- █ [Redacted list item]
- █ [Redacted list item]
- █ [Redacted list item]
- █ [Redacted list item]
- █ [Redacted list item]

3.5 Safety Analyses

3.5.1 Adverse Events and Serious Adverse Events

Adverse events will be coded with MedDRA version 21.0 or later. Analysis of adverse events will include the type, incidence, severity and relationship to study investigational product summarized by MedDRA System Organ Class (SOC) and Preferred Term (PT), by insulin strata and treatment group as well as overall. The AEs summaries will include only treatment-emergent AEs, i.e., those occurring after administration of investigational product. Subjects will be counted once for specific PT or MedDRA SOC when calculating incidence rates. If the same AE Preferred Term occurs multiple times within a subject, the highest severity and level of relationship observed will be reported. Non-treatment-emergent AEs/serious adverse events (SAEs) will be presented in the listings.

3.5.2 Adverse Events of Special Interest

The following AESIs have been identified for this protocol: hepatic function abnormality meeting the definition of Hy's law, which is defined as any increase in alanine aminotransferase (ALT) or aspartate aminotransferase (AST) to greater than 3x ULN and concurrent increase in total bilirubin to greater than 2x ULN. Concurrent findings are those that derive from a single blood draw or from separate blood draws taken within 8 days of each other.

The AESIs will be summarized overall, as well as categorized by MedDRA system organ class and preferred term by insulin strata and treatment.

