4.1.6 Discontinuation of Investigational Product

An individual subject will not receive any further investigational product if any of the following occur in the subject in question:

- 1 Withdrawal of consent from further treatment with investigational product
- 2 Lost to follow-up
- 3 An AE that, in the opinion of the investigator or the sponsor, warrants discontinuation of further dosing; specific examples include:
 - Dose-limiting symptoms with respect to GI tolerability and in particular if a subject requires intravenous fluids to treat volume depletion secondary to nausea and vomiting, even after measures are taken to reduce the risk of vomiting, after discussion with the medical monitor
 - $eGFR \leq 25 \text{ mL/min/1.73 m}^2$ on two consecutive blood tests
 - Acute kidney injury (AKI) in a subject as defined by:
 - An increase in serum creatinine by 0.3 mg/dL (26.5 $\mu\text{mol/L}$) within 48 hours in at least 2 readings
 - An increase in serum creatinine to 1.5 times baseline in at least 2 readings, which is known or presumed to have occurred within the prior 7 days
 - Subject noncompliance that, in the opinion of the investigator or sponsor, warrants withdrawal (eg, refusal to adhere to scheduled visits).
 - Pregnancy in a female subject
 - Subjects with persistent fasting glucose level of $> 260 \text{ mg/dL}$ (14.4 mmol/L) despite a MTD of rescue therapy to enable optimisation of the subject's glycaemic control
 - Any subject where Hy's Law criteria on liver function tests is met: AST or ALT $\geq 3 \times$ ULN **together with** Total bilirubin $\geq 2 \times$ ULN
 - Any subject who develops a life-threatening arrhythmia including sustained ventricular tachycardia, ventricular fibrillation or new ECG changes of second or third-degree heart block

Subjects who are permanently discontinued from receiving investigational product will be followed for protocol-specified assessments including follow-up of any AEs unless consent is withdrawn from further study participation (Section 4.1.5), the subject is lost to follow-up, the subject starts alternative treatment, or the subject is enrolled in another interventional clinical study.

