4.3.3 Clinical Laboratory Tests

A Laboratory Manual will be provided to the sites that specifies the procedures for collection, processing, storage, and shipment of samples, as well as laboratory contact information, specific to this clinical research study.

Clinical laboratory safety tests will be performed in a licensed central clinical laboratory. Urine pregnancy tests may be performed at the site using a licensed test (urine human chorionic gonadotropin [hCG]; dipstick). Abnormal laboratory results should be repeated as soon as possible (preferably within 24 to 48 hours).

The following clinical laboratory tests will be performed (see [Table 9](#), [Table 10](#), [Table 11](#) for the schedule of tests):

Serum Chemistry

Sodium	Bicarbonate
Potassium	Aspartate transaminase (AST)
Chloride	Phosphorus
Glucose	Blood urea nitrogen (BUN) or serum urea
Creatinine	Alkaline phosphatase (ALP)
Albumin	Alanine transaminase (ALT)
Calcium	Total bilirubin
Magnesium	

Hematology

Hematocrit	Platelet count
Hemoglobin	Mean corpuscular hemoglobin concentration
Red blood cells (RBC)	Mean corpuscular volume
White blood cells (WBC) count with differential	

Urinalysis

pH	Specific gravity
Bilirubin	Color
Glucose	Appearance
Ketones	WBC Casts
Blood	RBC Casts
Protein	

Note: Urinalysis for protein, glucose, ketones, and blood may be performed at the site using a licensed test (dipstick).

Pregnancy Test (females of childbearing potential only)

- Urine human chorionic gonadotropin (hCG)

Other Tests

- Urine albumin / creatinine ratio
- Urine drug screen (screening and Day -5 only)
- Alcohol screening test (screening and Day -5 only)
- Pancreatic amylase, lipase
- Calcitonin
- Lactate
- HIV-1 and -2 antibodies (screening only)
- Hepatitis B and C serology (screening only)
- Fasting lipid profile

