5.3.1 Hepatic Function Abnormalities

Refer to Section 5.6.2 and Section 10.5 for the definition and follow-up for liver abnormalities. There are no other AESIs in this study.

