10.5.1 Introduction

This appendix describes the process to be followed to identify and appropriately report cases of Hy's Law. It is not intended to be a comprehensive guide to the management of elevated liver biochemistries.

During the course of the study, the investigator will remain vigilant for increases in liver biochemistry. The investigator is responsible for determining whether a subject meets potential Hy's Law criteria at any point during the study.

The investigator participates, together with MedImmune clinical project representatives, in review and assessment of cases meeting potential Hy's Law criteria to agree whether Hy's Law criteria are met. Hy's Law criteria are met if there is no alternative explanation for the elevations in liver biochemistry other than drug-induced liver injury (DILI) caused by the investigational product.

The investigator is responsible for recording data pertaining to potential Hy's Law/Hy's Law cases and for reporting AEs and SAEs according to the outcome of the review and assessment in line with standard safety reporting processes.

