10.5.2 Definitions

Potential Hy's Law

AST or ALT $\geq 3 \times$ ULN together with TBL $\geq 2 \times$ ULN at any point during the study following the start of study medication irrespective of an increase in alkaline phosphatase (ALP).

Hy's Law

AST or ALT $\geq 3 \times$ ULN **together with** TBL $\geq 2 \times$ ULN, where no other reason, other than the investigational product, can be found to explain the combination of increases; eg, elevated ALP indicating cholestasis, viral hepatitis, or another drug.

For potential Hy's Law and Hy's Law, the elevation in transaminases must precede or be coincident with (ie, on the same day) the elevation in TBL, but there is no specified timeframe within which the elevations in transaminases and TBL must occur.

Identification of Potential Hy's Law Cases

In order to identify cases of potential Hy's Law, it is important to perform a comprehensive review of laboratory data for any subject who meets any of the following identification criteria in isolation or in combination:

- $ALT \geq 3 \times ULN$
- $AST \geq 3 \times ULN$
- $TBL \geq 2 \times ULN$

The investigator will without delay review each new laboratory report and if the identification criteria are met will:

- Notify the sponsor study representative
- Determine whether the subject meets PHL criteria by reviewing laboratory reports from all previous visits
- Promptly enter the laboratory data into the laboratory eCRF

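### SAP 3.5.2 defines Hy's law, the trial's only AESI, differently from Protocol 10.5.2, so the AESI summary may not match the cases identified under the protocol

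*SAP*

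**What the plan says.** Protocol 5.3 makes a hepatic abnormality meeting Hy's Law an AESI and points to Section 5.6.2 for its definition. Protocol 5.3.1 says there are no others and directs: "Refer to Section 5.6.2 and Section 10.5 for the definition and follow-up for liver abnormalities".

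Protocol 10.5.2 defines two tiers. Potential Hy's Law is the laboratory pattern after the start of study medication: AST or ALT at or above 3x ULN together with total bilirubin (TBL) at or above 2x ULN. Hy's Law is that pattern with no cause other than the investigational product. On order, the rule for both tiers is that "the elevation in transaminases must precede or be coincident with (ie, on the same day) the elevation in TBL". On the interval separating these two findings, the same section is explicit that "there is no specified timeframe within which the elevations in transaminases and TBL must occur". Section 10.5.1 repeats the cause condition, under which a case counts as Hy's Law only "if there is no alternative explanation for the elevations in liver biochemistry other than drug-induced liver injury (DILI") from the study drug.

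SAP 3.5.2 names the same AESI but writes its own definition and does not cite Protocol 10.5. It requires ALT or AST greater than 3x ULN and a concurrent bilirubin greater than 2x ULN, and then specifies: "Concurrent findings are those that derive from a single blood draw or from separate blood draws taken within 8 days of each other". The AESIs are to be summarised overall and "categorized by MedDRA system organ class and preferred term by insulin strata and treatment".

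**The concern.** The protocol deals with both timing and order, so the SAP is not filling a gap; it states a different rule. A subject could therefore be a potential Hy's law case for the investigator and absent from the AESI table, or be in the table without meeting the protocol definition. The SAP also has a single category where the protocol has two, so an elevation with an agreed alternative cause would be tabulated as Hy's law.

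No other summary described in the SAP clearly covers this. SAP 3.5.4 classifies chemistry results as low, normal or high and describes no table of combined transaminase and bilirubin multiples of ULN. With about 40 subjects planned, one case classified differently would change the trial's only AESI result.

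**Working it through.** The plan gives no figure to reproduce here. The check compares the definitions clause by clause and then applies each to the visit schedule.

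**Definitions side by side**

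| Element | Protocol 10.5.2 | SAP 3.5.2 |
|---|---|---|
| Transaminase (ALT or AST) | >= 3x ULN | > 3x ULN |
| Bilirubin | >= 2x ULN | > 2x ULN |
| Time between elevations | no limit | same draw, or within 8 days |
| Order | transaminase first or same day | none stated |
| Cause | potential Hy's Law: none; Hy's Law: no other explanation | none stated |

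The threshold difference matters only at exactly 3x or 2x.

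**Scheduled draws.** Protocol Tables 10 and 11 place post-dose serum chemistry on Days 5, 12, 19, 32, 33, 40±5 and 60±5 (Day 1 is predose). Section 4.3.3 shows that each chemistry draw includes ALT, AST and total bilirubin.

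**Gaps between consecutive draws (nominal days).**
- 12-5 = 7; 19-12 = 7; 32-19 = 13; 33-32 = 1; 40-33 = 7; 60-40 = 20. Two of the six exceed 8 days.
- With visit windows, Day 33 to Days 35-45 is 2 to 12 days, so it can also exceed 8. Days 35-45 to Days 55-65 is 10 to 30 days, so it always does.

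**Pairs of different days.** There are 7 x 6 / 2 = 21. Those within 8 days are 5/12 (7), 12/19 (7), 32/33 (1), 32/40 (8) and 33/40 (7), which makes 5; the other 16 exceed 8 days. If the Day 40 visit falls on Day 45, only 3 remain.

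**Timing rules only, over all 7 x 7 = 49 combinations of transaminase day and bilirubin day.**
- Protocol (transaminase on or before bilirubin): 7 same-day + 21 = 28.
- SAP (8 days or less, either order): 7 same-day + 2 x 5 = 17.
- Both: 7 + 5 = 12. Protocol only: 28 - 12 = 16. SAP only: 17 - 12 = 5.

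These are counts of calendar combinations, not probabilities. The different-day counts bear on a subject only if the two elevations never share a draw.

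**Illustrative subjects under the two laboratory rules (all values are multiples of ULN; AST is taken as not qualifying)**

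| Case | Protocol potential Hy's law | SAP |
|---|---|---|
| A. ALT 4x on Day 19; ALT 2.5x and bilirubin 2.5x on Day 32 | yes | no |
| B. As A, but ALT 3.5x on Day 32 | yes | yes |
| C. As A, plus a repeat on Day 24 with ALT 3.2x (32-24 = 8 days) | yes | yes |
| D. Bilirubin 2.5x on Day 5; ALT 4x and bilirubin 1.5x on Day 12 | no | yes |
| E. Exactly 3.0x and 2.0x on one draw | yes | no |

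A and D show that the rules disagree in both directions on scheduled visits. B and C show how easily a miss is avoided. The cause difference does not depend on the calendar: a same-draw elevation with an agreed alternative cause is Hy's law under the SAP and not under Protocol 10.5.2.

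**Amendments.** The SAP introduction cites Protocol Amendment 2 and a German local amendment. The protocol's logs for Amendments 3 and 4 list no change to Section 10.5.

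**The case against.** The best counter-argument is that the table is meant to show reported events. SOC and preferred term belong to coded adverse events; Protocol 5.3 has AESIs entered in the eCRF; and Section 10.5.4 supplies report terms for both Hy's Law and Potential Hy's Law. On that reading the protocol selects the cases and the SAP definition may change no count. This is plausible and lowers the risk. But the SAP does not say so, and a programmer given a laboratory definition with an 8-day window could reasonably apply it to laboratory data. The programming plan that might settle the matter was not available.

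Second, the protocol is itself mixed on cause. Section 4.1.6 refers to Hy's "Law criteria on liver function tests is met: AST or ALT" with the laboratory multiples alone, and Section 5.6.2 gives the same pattern before referring to 10.5. This weakens the cause point. It does not touch the window or the order rule, and Sections 10.5.1 and 10.5.2 are clear about cause.

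Third, missed cases should be few. All three analytes come from each draw, and Protocol 4.3.3 asks: "Abnormal laboratory results should be repeated as soon as possible (preferably within 24 to 48 hours"). This stands, and it limits the size of the problem.

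Fourth, the amendment evidence is not complete. The German local amendment was not available, and the Amendment 3 log lists key changes only. The supplied texts nevertheless conflict.

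**Conclusion.** SAP 3.5.2 is wrong as written. It departs from Protocol 10.5.2 on time window, order and threshold inclusiveness, and it does not separate potential from confirmed Hy's law. The textual conflict is certain. Whether any count changes depends on the table being built from laboratory data and on a subject whose elevations fall outside one rule but inside the other, or who has another agreed cause.

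The consequence is limited to a descriptive summary. No hypothesis test or primary result is affected, and identification, review and SAE reporting of cases follow the protocol. No expected number of misclassified cases can be derived from the documents. The correction is still worth making, because this is the study's only AESI and the table should agree with the reported cases.

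**What to change.** Reconcile SAP 3.5.2 with Protocol 10.5.2 for the analysis definition: the same inclusive thresholds, the same order rule and no time window, preferably by citing that section. Tabulate potential Hy's law (laboratory criteria) separately from Hy's law after the protocol's cause review. State for each count whether it comes from laboratory data or from reported events.

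This concerns the analysis definition only and leaves the discontinuation rule in Protocol 4.1.6 alone. The cost is SAP wording and minor programming, with no new data.

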3.5.3 Deaths and Treatment Discontinuations due to Adverse Events

A listing of any deaths will be provided which will include the MedDRA SOC and PT. AEs resulting in permanent discontinuation of study drug will be summarized by insulin strata and

treatment. The summary will include results summarized overall and by MedDRA System Organ Class and Preferred Term.

3.5.4 Clinical Laboratory Evaluation

Hematology, serum chemistry, and urinalysis laboratory evaluations will be performed during the study. The hematology and serum chemistry (including calcitonin, lipase, and amylase) parameters as well as their changes from baseline will be summarized with descriptive statistics (number of subjects, mean, and standard deviation, median, minimum and maximum) by insulin strata and treatment group. Other laboratory parameters collected will be summarized in a similar manner. The hematology and serum chemistry results will also be classified as low, normal, or high. The urinalysis results will be classified as normal or abnormal. The shift from baseline hematology, serum chemistry, and urinalysis results will be summarized by insulin strata and treatment at each evaluation time.

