4.1.2 Inclusion Criteria

Subjects must meet all of the following criteria:

- 1 Age ≥ 18 and < 85 years at screening.
- 2 Signed and dated written informed consent (with the exception of consent for genetic and nongenetic research) prior to performing any protocol-related procedures, including screening evaluations.
- 3 Diagnosed with T2DM with glucose control managed with any insulin*¹ and/or oral therapy combination where no significant dose changes of oral therapy of more than 50% have occurred in the 3 months prior to screening
- 4 Body mass index (BMI) between 25 and 45 kg/m² (inclusive) at screening
- 5 HbA1c range of 6.5 % to 10.5% (inclusive) at screening
- 6 Renal impairment with eGFR ≥ 30 and < 60 mL/min/1.73 m² at screening. Approximately 16 subjects (40%) are required to have a screening eGFR ≥ 30 and < 45 mL/min/1.73 m² and at least 16 subjects (40%) are required to have screening eGFR ≥ 45 and < 60 mL/min/1.73 m². eGFR will be determined by the chronic kidney disease-epidemiology collaboration (CKD-EPI) equation. In instances where the eGFR estimated during the screening period is outside the range expected from the subject's medical history, the subject may be re-tested once.
- 7 Females of childbearing potential must have a negative pregnancy test at screening and randomisation, and must not be lactating. Women of childbearing potential who are sexually active with a nonsterilized male partner must be using at least one highly effective method of contraception (see Section 10.2 for definition of females of childbearing potential and for a description of highly effective methods of contraception) from screening and up to 4 weeks after the last dose of investigational product. It is strongly recommended for the male partner of a female subject to also use male condom plus spermicide throughout this period. Cessation of contraception after this point should be discussed with a responsible physician. Periodic abstinence, the rhythm method, and the withdrawal method are not acceptable methods of contraception.

*¹ At least 50% of subjects (n=20) enrolled in the study should be taking insulin at a total daily dose of ≥ 20 units.

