4.8.4.2 Analysis of Clinical Laboratory Parameters

Laboratory parameters will be assessed at baseline as well as throughout the study. Frequencies of abnormal laboratory measurements will be presented for each laboratory parameter. Also, laboratory parameters will be assessed by presenting tables containing information related to laboratory shifts from baseline relative to the normal range, as well as descriptively over time.

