3 STATISTICAL METHODS

3.1 General Considerations

Data will be presented in data listings sorted by insulin strata, treatment, subject number and date collected, where appropriate. Tabular summaries will be presented for each treatment and for insulin strata within treatment. Categorical data will be summarized by treatment and for insulin strata within each treatment with the number and percentage of subjects within each category. In general, continuous variables will be summarized by treatment and insulin strata within treatment with descriptive statistics including mean, standard deviation, median, minimum, and maximum. Safety variables will generally be summarized by treatment across insulin strata.

All available data will be included in the analyses and missing data will not be imputed except as specified in the calculation of the AUC values. Unless specified otherwise, baseline values will be defined as the last valid assessment prior to the first administration of study medication.

All statistical tests will be 2-sided at an alpha = 0.10 significance level unless stated otherwise. There will be no adjustment for multiplicity.

Data analyses will be performed using SAS[®] version 9.3 or higher (SAS Institute Inc., Cary, NC) in a UNIX environment. The analytical results generated from SAS programs will follow MedImmune SAS programming standards and will be validated according to MedImmune SAS validation procedures.

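### Low/normal/high shift tables are uninformative for worsening of eGFR, and of creatinine already above its upper limit, and no readable table counts subjects crossing the protocol's eGFR cut points

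*SAP*

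**What the plan says.** SAP 3.5.4 sets the categorical scale: "The hematology and serum chemistry results will also be classified as low, normal, or high". Urinalysis is graded normal or abnormal. The section continues: "The shift from baseline hematology, serum chemistry, and urinalysis results will be summarized by insulin strata and treatment at each evaluation time". Protocol 4.8.4.2 promises frequencies of abnormal values for each parameter, and "laboratory shifts from baseline relative to the normal range, as well as descriptively over time".

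SAP 3.5.4 also plans a continuous summary, in which the "parameters as well as their changes from baseline will be summarized with descriptive statistics" (number, mean, SD, median, minimum, maximum).

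Inclusion criterion 6 in Protocol 4.1.2 reads: "Renal impairment with eGFR ≥ 30 and < 60 mL/min/1.73 m² at screening". Protocol Tables 10 and 11 schedule eGFR as part of serum chemistry.

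The protocol uses its own renal thresholds for managing subjects:

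- Section 3.1.4 acts on eGFR 30-44, below 30, and 25 or less.
- Section 4.1.6 lists eGFR of 25 or less on two consecutive tests.
- Section 4.1.6 also lists two acute kidney injury criteria, one of them "An increase in serum creatinine to 1.5 times baseline in at least 2 readings", with a time condition attached.

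No readable part of the SAP tabulates any of these.

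**The concern.** A three-level scale can show harm only if subjects start with a worse level still open to them. Here the entry rule selects subjects on a renal marker that is already reduced, and low is the worst level for eGFR.

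The safety profile in type 2 diabetes with renal impairment is a secondary objective, and laboratory results are a named endpoint (Protocol 2.2). A natural question for this trial is how many subjects in each arm fell below 30, or to 25 or less. The categorical tables, as specified, do not answer it. A row showing almost everyone as low to low could be misread as stability.

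**Working it through.** The plan gives no figure on this point to reproduce. Its one design calculation, power for the primary endpoint, does not bear on it.

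**1. eGFR.** The documents give no reference range. Assume a lower normal limit of 60 or of 90; both give the same result below. The last column uses the protocol's cut points of 45, 30 and 25.

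| eGFR change | Decline | Low/normal/high | Protocol bands |
|---|---|---|---|
| 59 to 45 | 14/59 = 24% | low to low | no band change |
| 59 to 30 | 29/59 = 49% | low to low | 45-59 to 30-44 |
| 59 to 25 | 34/59 = 58% | low to low | 45-59 to 25 or less |
| 45 to 30 | 15/45 = 33% | low to low | 45-59 to 30-44 |
| 45 to 25 | 20/45 = 44% | low to low | 45-59 to 25 or less |
| 32 to 24 | 8/32 = 25% | low to low | 30-44 to 25 or less |
| 30 to 25 | 5/30 = 17% | low to low | 30-44 to 25 or less |

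The planned scale registers none of the seven declines. The bands register six. The first row shows why the continuous change is still needed.

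eGFR is scheduled with serum chemistry but is absent from the analyte list in Protocol 4.3.3, so it may not be classified at all. In that case there is no categorical eGFR summary, and the gap is the same.

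**2. Which baseline applies.** Entry uses the screening value, but SAP 3.1 says "baseline values will be defined as the last valid assessment prior to the first administration of study medication". Some subjects could therefore start at 60 or above. For illustration, assume that true eGFR is uniform on 25-75 and that screening and pre-dose readings vary independently around it. Among subjects screened at 30 to below 60, the share with a pre-dose value of 60 or more is:

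- within-subject CV 5%: 5.6%, or 40 × 0.056 = 2.2 subjects
- CV 8%: 9.0%, or 3.6 subjects
- CV 12%: 13.2%, or 5.3 subjects

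With a lower limit of 60, those few could shift from normal to low. The rest could not worsen on the scale.

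**3. Creatinine.** No upper limit (ULN) is given, so work in multiples of it. A 1.5-fold rise appears as normal to high only if baseline ≤ ULN and 1.5 × baseline > ULN, that is, if baseline lies above 1/1.5 = 0.67 and up to 1.0 × ULN.

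- 0.8 × ULN rises to 1.2: seen
- 1.0 × ULN rises to 1.5: seen
- 1.1 × ULN rises to 1.65: high to high, not seen
- 1.3 × ULN rises to 1.95: high to high, not seen

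How many subjects start above ULN depends on assumptions. The protocol names CKD-EPI; take the 2009 version, ages 55-84, and ULNs of 1.3 mg/dL (men) and 1.1 mg/dL (women). Then eGFR 45 corresponds to 1.42-1.68 mg/dL in men and 1.12-1.33 in women, all above ULN. eGFR 59 corresponds to 1.14-1.34 and 0.90-1.06, so all these women and most of these men are in range. The margin is thin: with a ULN of 1.2 for women, the 1.12 case is in range too.

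**4. What the continuous summary adds.** A fall of 8 units in one of 20 subjects moves the arm mean by 8/20 = 0.4. The minimum and maximum show the most extreme subject, not how many crossed a cut point. A change of −8 also means different things from 58 and from 32.

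**The case against.** The strongest reply is that renal worsening is visible elsewhere, and much of this stands:

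- SAP 3.5.4 gives changes from baseline with extremes, and SAP 3.1 gives listings by treatment and subject. With about 20 subjects per arm, a large fall would be noticed.
- Protocol 4.1.6 names confirmed eGFR of 25 or less and acute kidney injury as examples of adverse events warranting discontinuation of investigational product. Such cases should reach the tables in SAP 3.5.1 and 3.5.3.
- Protocol 5.1 requires laboratory findings that need medical intervention, or are judged medically significant, to be reported as adverse events.
- Exploratory endpoints and SAP 3.4.3 are redacted, and table templates sit in a separate programming plan, so a renal table may exist that cannot be seen here.

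These routes do not give the count. Adverse event tables are organised by coded term and depend on the investigator's judgement; under Protocol 5.1, values judged not significant and not needing intervention are not reported. Discontinuation tables do not capture a single value of 25 or less, or a fall below 30, which in Protocol 3.1.4 leads to changes in other medication but not in itself to stopping the investigational product.

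A reader might infer more: that the shift tables cannot show renal worsening at all, or that the plan would report no renal change in either arm. The documents do not support that. Creatinine that starts in range can shift to high, at least 16 subjects are to have eGFR 45-59, and the outputs above remain. Nor does the argument carry over to serum glucose or dipstick results. An entry HbA1c of 6.5% or more does not put any one glucose reading out of range, and no entry criterion requires protein or glucose in the urine.

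**Conclusion.** The point holds in limited form. In the readable plan, the only categorical laboratory summaries are abnormal-value frequencies and shifts against the normal range. They are uninformative for worsening of eGFR in subjects who start below the lower limit, and of creatinine in subjects who start above ULN. No readable table counts subjects by arm who cross the protocol's eGFR cut points.

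For eGFR, this affects all subjects below 60 at baseline if the lower limit is 60 or more. Under the illustrative assumptions, that is all but about 2 to 5 of 40 for a limit of 60. For creatinine, the affected share cannot be fixed from the documents.

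The consequence is an incomplete safety display, not a failure to detect renal harm. The finding rests on the assumed eGFR limit and on what is legible.

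**What to change.** Keep the standard shift and abnormal-frequency tables: Protocol 4.8.4.2 promises them, and normal-to-high creatinine shifts are informative. Add to SAP 3.5.4, by treatment, at each visit and for the worst on-treatment value:

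1. A shift from baseline by eGFR band at the protocol's cut points: ≥ 60, 45 to < 60, 30 to < 45, > 25 to < 30, and ≤ 25. Written this way, no value falls between bands.
2. Counts of subjects meeting the Protocol 4.1.6 renal criteria exactly as written: eGFR ≤ 25 on two consecutive tests, and both creatinine criteria with their repeat-reading and time conditions. Any count of single readings at ≥ 1.5 × baseline should be labelled unconfirmed.

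Unscheduled repeats should be included. Scheduled on-treatment chemistry falls on Days 1, 5, 12, 19 and 32, at gaps of 4, 7, 7 and 13 days. Only Days 32 and 33 lie within 48 hours of each other, so the 48-hour criterion depends largely on repeats. Serum glucose and dipstick summaries need no change.

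Cost: one or two descriptive tables with small cell counts, from data already collected. If a redacted section already holds such a table, a cross-reference from SAP 3.5.4 is enough.
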